15.3.1. SUPPORTIVE ANALYSIS TO EXPLORATORY EFFICACY ANALYSES

No supportive analyses will be performed for the exploratory efficacy endpoints.

Document:	\\quintiles.net\enterprise\Apps\sasdata\SASa\sas\AVID\18F-AV-1451\Biostatistics\Documentation\SAP\Avid_18F-AV-1451-A16_SAP_Final_v1.0_20180815.docx		
Author:	XXXXXXXXXX	Version Number:	Final, v1.0
		Version Date:	15Aug2018
Template No:	CS_TP_BS016 – Revision 3	Reference:	CS_WI_BS005
Effective Date:	01May2012		

15.3.2. SUBGROUP ANALYSES TO EXPLORATORY EFFICACY ANALYSES

No subgroup analyses will be performed for the exploratory efficacy endpoints.

15.4. OTHER EFFICACY

To evaluate the intra-rater reliability of the ¹⁸F-AV-1451 PET scan interpretation, eleven images were randomly selected to be reviewed twice by each of the 5 readers. Given the limited number of images that were reviewed twice by each reader and that no stratification on the most recent neurological disease diagnosis was performed (to ensure balanced potentially TS negative cognitively normal and potentially TS positive dementia cases), no statistical inferences will be presented. That is, only frequencies will be provided for the intra-rater reliability.

15.4.1. SUPPORTIVE ANALYSIS TO OTHER EFFICACY ANALYSIS

No supportive analyses will be performed for the other efficacy endpoint.

15.4.2. SUBGROUP ANALYSES TO OTHER EFFICACY ANALYSIS

No subgroup analyses will be performed for the other efficacy endpoint.

16. SAFETY OUTCOMES

All outputs for safety outcomes will be summarized overall and by most recent neurological disease diagnosis based on the SAF.

16.1. ADVERSE EVENTS

AEs will be coded to the SOC and PT using the MedDRA central coding dictionary, version 18.1.

TEAEs are defined as AEs that started or worsened in intensity or frequency on or after an ¹⁸F-AV-1451 injection and up to 48 hours after the ¹⁸F-AV-1451 injection. APPENDIX 1 describes the handling of partial dates and/or times for AEs. In case it is not possible to determine if an AE is treatment emergent or not, the AE will be classified by the worst case; i.e. treatment emergent.

An overall summary of number and percentage of subjects within each of the categories described in the sub-sections below will be provided.

Listings will include all AEs.

Document:	\\quintiles.net\enterprise\Apps\sasdata\SASa\sas\AVID\18F-AV-1451\Biostatistics\Documentation\SAP\Avid_18F-AV-1451-A16_SAP_Final_v1.0_20180815.docx		
Author:	XXXXXXXXXX	Version Number:	Final, v1.0
		Version Date:	15Aug2018
Template No:	CS_TP_BS016 – Revision 3	Reference:	CS_WI_BS005
Effective Date:	01May2012		

16.1.1. ALL TEAEs

Incidence (frequencies and percentages) of TEAEs will be presented by SOC and PT, and also broken down further by maximum severity, relationship to study medication, and relationship to study procedures. In addition, incidence of TEAEs will be presented by PT only (i.e., not broken down by SOC). Subjects with multiple occurrences of a SOC/ PT will only be counted once for that SOC/PT in the tables. Summaries will be presented by alphabetical order of SOC and decreasing order of total frequency of PT.

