7.1.4. Additional PET Imaging

If death does not occur within nine months of the ¹⁸F-AV-1451 PET scan, the subject may be given the opportunity to undergo a second ¹⁸F-AV-1451 PET scan and continue in the protocol at the sponsor's discretion. In order to obtain a second scan before the nine month expiry date, it is recommended the second scan be performed any time between six and nine months after the first scan. If the subject agrees to a second ¹⁸F-AV-1451 PET scan, screening assessments will not be repeated. The procedures in Section 7.1.2 will be performed and updated medical history /concurrent medications and an updated neurological disease diagnosis (according to best available information) will be collected. If the subject subsequently comes to autopsy, the second scan (nearest to time of death) will be used in the efficacy analyses. Because cortical tau deposition is expected to occur very slowly, if at all, in cognitively normal (unimpaired) subjects, cognitively normal subjects will not be required to undergo repeat scans. Cognitively normal subjects will remain eligible for autopsy, regardless of time from first scan or second scan to autopsy, and will be included in the primary efficacy cohort if the subject comes to autopsy any time before the trial stopping criteria are met. Subjects of other cognitive status that do not consent to a second ¹⁸F-AV-1451 PET scan will not be included in the primary analyses unless death occurs within nine months of the initial scan.

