In order to control for the potential progressive change in tau deposition over time, cognitively impaired subjects for who death did not occur within nine months of the ¹⁸F-AV-1451 PET scan were given the opportunity to undergo a second ¹⁸F-AV-1451 PET scan and continue in the protocol at the Sponsor's discretion. In order to obtain a second PET scan before the nine month expiry date, it was recommended that the second scan be performed any time between six and nine months after the first scan. If the subject agreed to a second ¹⁸F-AV-1451 PET scan, screening assessments were not repeated with exception of any updates to the medical history/concurrent medications and an updated neurological disease diagnosis (according to best available information) which were collected at the time of the second ¹⁸F-AV-1451 PET imaging visit. If the subject subsequently came to autopsy, the data (neurological disease diagnosis and ¹⁸F-AV-1451 PET scan) from the second ¹⁸F-AV-1451 PET imaging visit (nearest to time of death) will be used in the analyses. Cognitively normal (unimpaired) subjects were not required to undergo repeat scans, even if death occurred more than nine months after the ¹⁸F-AV-1451 PET scan, because cortical tau deposition was expected to occur very slowly, if at all, in such subjects. That is, cognitively normal subjects remained eligible for autopsy, regardless of time from first or second scan to autopsy, and will be included in the Primary Efficacy Analysis Cohort if the subject came to autopsy at any time before the trial stopping criteria were met (refer to Section 7.1).

Up to the first 6 subjects that come to autopsy were to be considered as 'front-runners'. Avid were not blinded to the front-runner imaging and pathology results. These results were analyzed on a patient-by-patient basis and were used to refine the PET or autopsy methods (e.g., pathology staining, quantitation methods, etc.). Upon completion of the final front-runner subjects analysis, the final imaging and autopsy methods were specified. No additional PET image reads or autopsy analyses were performed until the PET image read and autopsy methods were finalized. The front-runners will not be included in the Primary

Document:	\\quintiles.net\enterprise\Apps\sasdata\SASa\sas\AVID\18F-AV-1451\Biostatistics\Documentation\SAP\Avid_18F-AV-1451-A16_SAP_Final_v1.0_20180815.docx		
Author:	XXXXXXXXXX	Version Number:	Final, v1.0
		Version Date:	15Aug2018
		Reference:	CS_WI_BS005

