5.2. SAFETY ANALYSIS SET

The safety analysis set (SAF) will be the same as ENR i.e., include all subjects who provided informed consent and received at least one ¹⁸F-AV-1451 injection.

This analysis set will be used to summarize demographic and other baseline characteristics (refer to Section 10), medical/surgical history, concurrent medical conditions/diseases, family neurological disease history, and subjects neurological disease history (refer to Section 11), concomitant medications (refer to Section 12), cognition assessments at screening (refer to Section 13), exposure to ¹⁸F-AV-1451 (refer to Section 14), and all safety data (refer to Section 16). Summaries will be presented overall and by most recent neurological disease diagnosis.

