6.3. REPEATS, UNSCHEDULED VISITS AND EARLY TERMINATION DATA

In order to control for the potential progressive change in tau deposition over time, cognitively impaired subjects for whom death did not occur within nine months of the ¹⁸F-AV-1451 PET scan were given the opportunity to undergo a second ¹⁸F-AV-1451 PET scan and continue in the protocol at the Sponsor's discretion. If the subject agreed to a second ¹⁸F-AV-1451 PET scan, screening assessments were not repeated with exception of any updates to the medical history/concurrent medications and an updated neurological disease diagnosis (according to best available information) which were collected at the time of the second ¹⁸F-AV-1451 PET imaging visit. If the subject subsequently came to autopsy, the data (neurological disease diagnosis and ¹⁸F-AV-1451 PET scan) from the second ¹⁸F-AV-1451 PET imaging visit

Document: \\quintiles.net\enterprise\Apps\sasdata\SASa\sas\AVID\18F-AV-1451\Biostatistics\Documentation\SAP\Avid_18F-AV-1451-A16_SAP_Final_v1.0_20180815.docx

Author: XXXXXXXXXX	Version Number: Final, v1.0
	Version Date: 15Aug2018
	Reference: CS_WI_BS005

Template No: CS_TP_BS016 – Revision 3
Effective Date: 01May2012

Copyright © 2012 Quintiles Transnational Corp. All rights reserved.

The contents of this document are confidential and proprietary to Quintiles Transnational Corp. Unauthorized use, disclosure or reproduction is strictly prohibited.

(nearest to time of death) will be used in the analyses. Cognitively normal (unimpaired) subjects were not required to undergo repeat scans, even if death occurred more than nine months after the ¹⁸F-AV-1451 PET scan, because cortical tau deposition is expected to occur very slowly, if at all, in such subjects. That is, cognitively normal subjects remained eligible for autopsy, regardless of time from first or second scan to autopsy. The safety analyses will include data from all scans.

This study does not accommodate unscheduled visits and no data will be collected at the time of an early termination beside the date and reason for discontinuation.

Listings will include scheduled, repeat, and early discontinuation data.

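### The adverse event tables pool all injections over a per-subject denominator, so diagnosis columns can differ through re-scanning alone; adding summaries by injection is a minor, cheap improvement.

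*SAP*

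**What the plan says.** The SAP defines a treatment-emergent adverse event (TEAE) as one that starts or worsens "on or after an ¹⁸F-AV-1451 injection and up to 48 hours after the ¹⁸F-AV-1451 injection" (SAP 16.1). Incidence is tabulated by system organ class and preferred term under the rule "Subjects with multiple occurrences of a SOC/ PT will only be counted once for that SOC/PT in the tables" (SAP 16.1.1). Injection site reactions are tabulated by preferred term (SAP 16.1.2). On repeat scans, SAP 6.3 states: "The safety analyses will include data from all scans". The safety set is to "include all subjects who provided informed consent and received at least one" injection (SAP 5.2), and SAP 16 adds: "All outputs for safety outcomes will be summarized overall and by most recent neurological disease diagnosis based on the SAF".

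On who is injected again, SAP 3.1 describes the second scan as an opportunity for "cognitively impaired subjects for who death did not occur within nine months of the" first scan, and then says "Cognitively normal (unimpaired) subjects were not required to undergo repeat scans". Protocol 7.1.4 agrees: "cognitively normal subjects will not be required to undergo repeat scans". The neurological diagnosis is updated at the second scan (SAP 3.1 and 6.3). A footnote to SAP 3.1 also lets either imaging visit be repeated after an invalid image, so more than two injections are possible.

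Net activity administered (SAP 14) and vital signs (SAP 16.4) are summarized separately for each injection. The SAP text specifies no such split for TEAEs or injection site reactions.

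**The concern.** A subject injected once has one 48-hour window in which a TEAE can arise, and a subject injected twice has two. The tables merge the windows and divide by subjects, so the percentage depends on how often a group was injected as well as on the risk at each injection. The design links re-injection to cognitive status, which is also the variable that defines the table columns.

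Enrollees are terminally ill, and Protocol 7.7.2 says that hospitalizations, complications and death are expected. Background events can fall into any window, whatever the tracer does. A reader who sees a higher percentage under dementia than under normal cognition could not tell from that table whether the risk per injection differed or only the number of injections. What is at stake is how a descriptive safety table is read.

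**Working it through.** The plan gives no TEAE rate, re-scan fraction or safety sample size, so it has no figure of its own to reproduce. The check shows how the tabulated percentage behaves.

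**Inputs**
- Window: 48 hours after each injection (SAP 16.1), so 48 hours for one injection and 96 for two.
- Denominator: subjects with at least one injection (SAP 5.2).
- p, the risk of at least one TEAE per injection: not in the documents, assumed 1% to 20%.
- f, the share of a diagnosis group injected twice: not in the documents, assumed 0% to 50%.
- Simplifications: at most two injections, with equal and independent risk at each.

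**Formulas**
- At least one TEAE in two injections: 1 − (1 − p)².
- Tabulated incidence: (1 − f)p + f[1 − (1 − p)²] = p[1 + f(1 − p)].
- Inflation relative to p: 1 + f(1 − p), which always stays below 2.
- Rate with injections as denominator: (1 + f)p / (1 + f) = p, whatever f is.

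**Results at p = 5%** (two injections: 1 − 0.95² = 9.75%)

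| f | Tabulated incidence | Ratio to p | Per-injection rate |
|---|---|---|---|
| 0% | 5.00% | 1.000 | 5.0% |
| 10% | 5.48% | 1.095 | 5.0% |
| 20% | 5.95% | 1.190 | 5.0% |
| 30% | 6.43% | 1.285 | 5.0% |
| 50% | 7.38% | 1.475 | 5.0% |

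At f = 30% the ratio runs from 1.24 (p = 20%) to 1.30 (p = 1%), so it depends far more on f than on p.

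**In counts.** Take 100 subjects, 30 of them injected twice, with p = 5%. Expected subjects with a TEAE: 70 × 0.05 + 30 × 0.0975 = 3.5 + 2.925 = 6.425, shown as 6.4%. A group of 100 with no second injections shows 5.0%. The gap is 1.4 percentage points with identical risk. Using injections instead, the first group has 130 injections and 130 × 0.05 = 6.5 expected injections with an event, and 6.5/130 = 5.0%.

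**Role of the once-per-term rule.** It is not the source of the effect. Counting every injection with an event over subjects would give p(1 + f) = 0.05 × 1.3 = 6.5%, slightly more than 6.43%. The effect comes from pooling all scans over a subject denominator.

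**Diagnosis label.** Columns use the most recent diagnosis. If a subject's diagnosis changes at the second scan, an event after the first injection is tabulated under the later label. A first-injection table that kept this grouping would still misplace such events.

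**The case against.** The strongest reply is that the SAP does what the protocol asks. Protocol 8.3 calls for AEs as the number and percentage of subjects affected, and SAP 16.1.1 delivers that. Subject-level incidence is conventional, and the SAP never presents it as a rate per administration. This stands: the table is valid as a subject-level summary and should stay.

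Second, nothing inferential depends on it. SAP 7.4 plans no testing of safety outcomes, and SAP 16 only summarizes by diagnosis. Under the model above, pooling raises the reported incidence and so would not hide a risk. This also stands.

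Third, a reader might infer that the tables will show more events in mild cognitive impairment and dementia than in normal subjects. The documents do not support that as a certainty. Normal subjects were not required to be re-scanned, but they were not barred; Protocol 5.1 offers the second scan without restriction by diagnosis, and Protocol 7.1.4 contemplates a second scan in normal subjects. Entry requires a projected life expectancy of at most six months, and a second scan needs the subject's agreement and the sponsor's discretion, so f could be small in every group. Repeats after an invalid image are not tied to diagnosis. A difference in f is likely from the design, but its size is unknown.

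Fourth, much can be reconstructed. Exposure is summarized for each injection by diagnosis, all AEs are listed, TEAEs are also split by relationship to study medication, and the table shells, which are not among these documents, might add a split. This lowers the stakes. It does not remove the point, because the SAP text requires no by-injection TEAE summary and a reader should not have to rebuild one from listings.

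**Conclusion.** The point holds in a limited form. The planned percentages are correct subject-level incidences, but they are not per-administration rates. Where the re-injected share differs between diagnosis groups, the columns can differ with no difference in risk per injection. The inflation is 1 + f(1 − p) under equal, independent risk and at most two injections. The 6.4% against 5.0% comparison rests on an assumed p of 5% and f of 30% against 0%, and it is an illustration, not an estimate. Equal risk is itself uncertain, because re-scanned subjects are those who survived long enough for a second scan; that is a further reason to show first and later injections separately.

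It would go too far to call the planned table an error, to say that it will show an excess in impaired subjects, or to say that it weakens the trial's conclusions. No hypothesis test or success criterion uses these tables. This is a minor improvement in presentation.

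**What to change.** Keep the per-subject tables. In SAP 16.1.1 and 16.1.2 add:
- TEAEs and injection site reactions after the first injection and after later injections, each with the subjects who received that injection as denominator;
- a per-injection total: injections followed by an event, divided by injections given;
- for the first-injection table, grouping by the diagnosis recorded at that injection, not the most recent one.

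This brings AEs into line with SAP 14 and 16.4. No new data are needed: injection date and time already drive the TEAE algorithm in SAP Appendix 2, and the diagnosis is updated at the second scan. The cost is a short change to the SAP text and slightly longer tables.

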16.1.1.1. Severity

Severity will be classified as mild, moderate or severe. TEAEs with a missing severity will be classified as severe. If a subject reports a TEAE more than once within a SOC/PT, the AE with the worst case severity will be used in the corresponding severity summaries.

16.1.1.2. Relationship to Study Medication

Relationship to study medication, as indicated by the Investigator on the eCRF, will be classified as related or not related to study medication. TEAEs with a missing relationship to study medication will be regarded as related to ¹⁸F-AV-1451. If a subject reports the same AE more than once within a SOC/ PT, the TEAE with the worst case relationship to ¹⁸F-AV-1451 will be used in the corresponding relationship summaries.

16.1.1.3. Relationship to Study Procedures

Relationship to study procedures, as indicated by the Investigator on the eCRF, will be classified as related or not related to study procedures. TEAEs with a missing relationship to study procedures will be regarded as related to study procedures. If a subject reports the same AE more than once within a SOC/ PT, the TEAE with the worst case relationship to study procedures will be used in the corresponding relationship summaries.

16.1.2. INJECTION SITE REACTIONS

Injection site reactions are those events that will be classified under the ‘Injection site reactions’ MedDRA High Level Term (HLT). Incidence of injection site reactions will be presented by PT. A listing containing all injection site reactions will also be prepared.

16.1.3. ADVERSE EVENTS WITH AN OUTCOME OF DEATH

AEs with an outcome of death are those events which have a resolution recorded as “Fatal” on the AEs page of the eCRF. Incidence of AEs with an outcome of death will be presented by SOC and PT. A listing containing all AEs with an outcome of death will also be prepared.

Document:	\\quintiles.net\enterprise\Apps\sasdata\SASa\sas\AVID\18F-AV-1451\Biostatistics\Documentation\SAP\Avid_18F-AV-1451-A16_SAP_Final_v1.0_20180815.docx		
Author:	XXXXXXXXXX	Version Number:	Final, v1.0
		Version Date:	15Aug2018
Template No:	CS_TP_BS016 – Revision 3	Reference:	CS_WI_BS005
Effective Date:	01May2012		

16.1.4. SERIOUS ADVERSE EVENTS

Serious adverse events (SAEs) are those events recorded as “Serious” on the AEs page of the eCRF. Incidence of SAEs will be presented by SOC and PT. A listing containing all SAEs will also be prepared.

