7.1. Assessment Periods

See Section 11.2, Trial Flow Chart

7.1.1. Screening Visit:

Screening may take place over several days and can occur at multiple locations (e.g. hospice, subject's home, research office, or clinic). All screening assessments will preferably be performed within 45 days prior to the PET imaging session. Some screening assessments may be performed on the imaging day prior to injection with sponsor approval. Screening assessments will include:

- 1. Informed consent (for clinical, imaging and autopsy procedures);
- 2. Obtain historical brain MRI images if available;
- 3. Demographics and baseline characteristics (e.g. birth year, gender, race, ethnicity, education);
- 4. Medical history and concomitant medications;
- 5. Brief physical and neurological exam;
- 6. Neurologic disease history (if relevant: date or months since symptom onset, date or months since diagnosis, family history of neurologic disease);
- 7. Mini-Mental Status Examination (MMSE) may be obtained if the subject is able to cooperate with the test;
- 8. Caregiver or informant to complete IQCODE;
- 9. Urine pregnancy test (for females of childbearing potential);
- 10. Vital signs, including the most recent height and weight which will be collected from subject's previous medical record; and
- 11. A physician or appropriate designee evaluation and summary of current medical status.

7.1.2. ¹⁸F-AV-1451 PET Imaging Visit(s):

- 1. The subject will be seen by a physician prior to dose administration who will assess their ability to safely tolerate the imaging procedure;
- Females of childbearing potential will have a urine (or serum if required by local IRB) pregnancy test prior to injection (the result must be negative for the subject to be administered ¹⁸F-AV-1451);
- 3. A target dose of 370 MBq (10 mCi) of ¹⁸F-AV-1451 will be administered intravenously and a 20-minute continuous brain PET imaging will begin 80 minutes post injection;
- 4. Images will be reconstructed and reviewed immediately after completion of the scan;
- 5. Vital signs will be taken immediately prior to administration of ¹⁸F-AV-1451, and after completion of imaging, prior to discharge;
- 6. Subjects will be observed continuously for signs of adverse events (AE) or serious adverse events (SAE). All AEs and SAEs will be followed until resolution;

- 7. The injection site will be observed for excessive inflammation or damage to the surrounding tissue where the dose was injected; and

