7.7.2. Adverse Event Definitions

Adverse Events

For reporting purposes, Avid will distinguish among pre-existing conditions, treatment emergent adverse events and trial-emergent adverse events. Pre-existing conditions (i.e., undesirable experiences, signs or symptoms that begin prior to the Screening Visit) will be recorded on the medical history and/or physical exam eCRF pages. Signs and symptoms that are believed to be due to the pre-existing condition (started prior to dose of investigational product) do not have to be recorded in the AEs section of the eCRF, unless there is an increase in frequency or severity. Additionally, signs or symptoms or changes in pre-existing conditions that occur outside the trial-defined adverse event reporting will be recorded in medical history.

An adverse event is any untoward medical occurrence associated with the use of a drug in humans, whether or not considered drug related. For the purposes of this study, untoward medical occurrences will be considered associated with the use of ¹⁸F-AV-1451, and thus be reported as treatment-emergent adverse events, if they occur within 48 hours after ¹⁸F-AV-1451 administration.

In the context of this study, adverse experiences including hospitalizations, medical complications and death are expected, since terminal illness is a requirement for entry into the study. Thus, if the investigator becomes aware of such events that occur after administration of the drug but outside the 48 hour reporting window, these will only be reported as adverse events if the investigator believes they are attributable to the investigational product or protocol procedure.

In order to capture possible adverse effects of trial participation, any untoward medical occurrences occurring after the informed consent until the administration of ¹⁸F-AV-1451 will be recorded in the CRF for reporting as trial-emergent adverse events. If the subject consents to a second ¹⁸F-AV-1451 PET scan, trial-emergent adverse events will be collected in a similar period, from either date of additional consent (if applicable) or the date the dose request for the second scan is submitted to Avid, up to the second administration of ¹⁸F-AV-1451.

Serious Adverse Event (SAE)

An SAE is an AE that results in one of the following outcomes or constitutes one of the following events:

- Death;

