7.7.4. Reporting of Serious Adverse Events

Study site personnel must alert Eli Lilly or its designee of any SAE within 24 hours of their awareness of the event via a sponsor-approved method. Alerts issued via telephone are to be immediately followed with official notification on study-specific SAE forms.

Serious adverse events occurring after a subject receives a dose of investigational product will be collected until 48 hours after the dosing of the investigational product, regardless of the investigator's opinion of causation. Therefore, SAEs that occur later than 48 hours after the dosing of the investigational product are not required to be reported unless the investigator feels the events were related to either investigational product or a protocol procedure.

If a subject experiences an SAE after signing informed consent(s), but prior to receiving investigational product, the event will be reported on the eCRF and to Eli Lilly or its designee. Previously planned (prior to signing the ICF) surgeries should not be reported

as SAEs unless the underlying medical condition has worsened during the course of the study.

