16.1.5. TEAEs LEADING TO DISCONTINUATION OF STUDY

TEAEs leading to discontinuation from study are those events with an action taken recorded as “permanently discontinued” on the AEs page of the eCRF. Incidence of TEAEs leading to discontinuation from study will be presented by SOC and PT. A listing containing all TEAEs leading to discontinuation from study will also be prepared.

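### The SAE and fatal-AE tables have no onset window, so the protocol's separation of trial-emergent from treatment-emergent events is lost in the tables and in the overall AE summary

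*SAP*

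**What the plan says.** SAP 16.1.4 defines its events by a flag: "Serious adverse events (SAEs) are those events recorded as “Serious” on the AEs page of the eCRF". The table rule follows: "Incidence of SAEs will be presented by SOC and PT". SAP 16.1.3 is built in the same way: "AEs with an outcome of death are those events which have a resolution recorded as “Fatal” on the AEs page of the eCRF", and "Incidence of AEs with an outcome of death will be presented by SOC and PT". No onset window appears in either section.

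Other AE tables in the SAP are restricted. SAP 16.1.1 covers TEAEs only, and SAP 16.1.5 says "Incidence of TEAEs leading to discontinuation from study will be presented by SOC and PT". SAP 16.1 defines a TEAE as an event that starts or worsens from an injection up to 48 hours after it. SAP 16.1 also promises one overall summary of subjects in each category of its subsections. SAP 16 runs all safety outputs on the safety set, which SAP 5.2 limits to consented subjects with at least one injection.

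Protocol 7.7.2 says that "Avid will distinguish among pre-existing conditions, treatment emergent adverse events and trial-emergent adverse events". It places trial-emergent events between consent and tracer administration. Before a second scan, a similar period runs from the additional consent or the dose-request date to the second injection. Protocol 7.7.4 brings pre-dose serious events into the data: "If a subject experiences an SAE after signing informed consent(s), but prior to receiving investigational product, the event will be reported on the eCRF". After dosing, SAEs are collected regardless of causality for 48 hours. Later ones need reporting only if the investigator relates them to the tracer or a protocol procedure.

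**The concern.** The safety set filters subjects, not events. A subject hospitalised between consent and injection, and injected afterwards, contributes that hospitalisation to the SAE table on the same footing as one that follows the tracer. The overall summary then puts TEAE counts limited to 48 hours next to SAE and fatal counts with no limit, and nothing in the SAP text tells the reader that the two cover different periods.

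The study has no control group, and Protocol 7.7.2 itself expects hospitalisations, complications and deaths because terminal illness is an entry requirement. Timing relative to injection is therefore one of the main ways to tell background serious events from those that might be associated with the tracer. The pre-dose period may also be much longer than the two-day post-dose window: "All screening assessments will preferably be performed within 45 days prior to the PET imaging session". If it is, the tabulated SAE incidence reflects length of screening and underlying illness as well as what happens after dosing. Any resulting error overstates serious events for the tracer.

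**Working it through.** The documents give no SAE count, rate or pre-dose share, so there is no plan figure to reproduce. The check has two parts.

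**1. Which events can enter each table**

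| Event | Safety set? | SAE table (16.1.4) | Fatal table (16.1.3) |
|---|---|---|---|
| SAE before the first injection, subject never injected | No | No | No |
| SAE before the first injection, subject later injected | Yes | Yes | Only if that event's outcome is death after an injection |
| Event in the run-up to a second injection | Yes, already injected once | Yes, if serious | Yes, if fatal |
| SAE within 48 hours after an injection | Yes | Yes | Yes, if fatal |
| SAE after 48 hours, attributed by the investigator | Yes | Yes | Yes, if fatal |

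So a death before any tracer was given cannot reach the fatal-AE table. Two routes remain: onset before the first injection with death after it, and events in the run-up to a second injection. The second route follows a first tracer dose.

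**2. How large the pre-dose share of tabulated SAEs could be**

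Inputs:
- Post-dose window: 48 hours = 2 days (Protocol 7.7.4, SAP 16.1).
- T, days from consent to first injection: not given. Protocol 7.1.1 offers only a soft 45-day limit for screening assessments, so T is varied.
- s, the share of pre-dose SAEs that occur in subjects who are still injected: not given, so it is varied. A physician must judge before dosing whether the subject can tolerate imaging (Protocol 7.1.2), so s may be well below 1.
- Assumptions: constant background SAE rate, no tracer effect, one injection, and no late attributed SAEs.

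Expected SAEs are then proportional to time at risk, and the rate cancels:

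pre-dose share = s × T / (s × T + 2)

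| T (days) | s | Calculation | Share |
|---|---|---|---|
| 0 (same day) | any | 0 / 2 | near 0% |
| 1 | 1 | 1 / 3 | 33% |
| 2 | 1 | 2 / 4 | 50% |
| 7 | 1 | 7 / 9 | 78% |
| 7 | 0.5 | 3.5 / 5.5 | 64% |
| 14 | 1 | 14 / 16 | 88% |
| 14 | 0.1 | 1.4 / 3.4 | 41% |
| 45 | 0.1 | 4.5 / 6.5 | 69% |
| 45 | 1 | 45 / 47 | 96% |

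The share passes one half when s × T exceeds 2 days: T above 2 days at s = 1, above 4 days at s = 0.5, and above 20 days at s = 0.1. If late attributed SAEs were as many as those inside the 48 hours, the denominator would gain another 2 and the top figure would fall to 45 / 49 = 92%.

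The formula counts events. An incidence table counts subjects, so a subject with both a pre-dose and a post-dose SAE appears once in the total.

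**The case against.** The strongest reply is that the SAP does what the protocol's analysis section asks. Protocol 8.3 says that all subjects with SAEs are to be summarised and states no window. Protocol 7.7.2 classifies events for reporting and does not prescribe table columns. This stands. A reader might infer that the SAP contravenes the protocol, but the documents do not support that: an all-SAE table is consistent with 8.3, and the gap is that the classes in 7.7.2 are not carried through.

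A second reply is that the information survives. All TEAEs, serious or not, are tabulated by severity and relationship (SAP 16.1.1), all SAEs and fatal AEs are listed, and Study Day is shown relative to the first injection (SAP 6.1). This also stands, so it would be wrong to call the serious-safety data uninterpretable. But the separation then has to be rebuilt line by line, and the incidence tables will not show it. Nor does pooling hide harm, since it can only add events.

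Third, the table shells are not in the documents and could add a restriction. The SAP also names protocol amendment 3 as its basis, whereas the protocol at hand is amendment 2. Neither possibility can be excluded. Even so, the SAP uses the TEAE label in 16.1.1 and 16.1.5 and omits it in 16.1.3 and 16.1.4, so on its text the scopes differ.

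Finally, these are descriptive tables with no hypothesis test (SAP 7.4), and no efficacy conclusion depends on them.

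**Conclusion.** The point holds as one of presentation by timing. As written, SAP 16.1.4 and the overall summary pool pre-dose SAEs of subjects later injected with post-injection SAEs. SAP 16.1.3 does so by the two narrower routes shown above, and the SAP has no trial-emergent category in which to show them apart.

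The size is unknown. A reader might infer from the 45-day screening allowance that most tabulated SAEs will predate dosing. The documents do not establish this. The 45 days is a preference for screening assessments, not an observed interval from consent to injection, and the share depends equally on how many subjects with a pre-dose SAE go on to be injected. The range runs from near 0% with same-day injection, through 33% at 1 day and 78% at 7 days (both s = 1) and 41% at 14 days with s = 0.1, to 96% at 45 days with s = 1. All of these rest on a constant background rate and no tracer effect.

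The change is worth making because the population is terminally ill and uncontrolled, and the SAE incidence is a figure that readers will attach to the tracer.

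**What to change.** Amend SAP 16.1.3 and 16.1.4 as follows.

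- Keep the all-SAE and all-fatal totals, which satisfies Protocol 8.3.
- Beside each total, add three columns: trial-emergent (consent, or the second-scan start point in Protocol 7.7.2, to injection); treatment-emergent (injection to 48 hours, as SAP 16.1 defines it); and later events that the investigator attributes to the tracer or a protocol procedure.
- Apply the partial-date rules of SAP Appendix 2. Add one rule that divides events classed as not treatment-emergent into those before an injection and those after 48 hours. State which column takes an event that falls in the run-up to a second injection but is attributed to the first.
- In the overall AE summary of SAP 16.1, show the treatment-emergent and later-attributed counts separately from the trial-emergent count. Limiting that summary to treatment-emergent events would drop late attributed SAEs, which Protocol 7.7.4 deliberately retains.

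The cost is minor SAP wording and programming, using event and injection dates and times already collected. No total changes.
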